## Randomization process

Randomization will be carried out at the time the patient presents for the intervention (in consultation, when the indication is made), after she has read and signed the informed consent. At this time, you will be randomly assigned to one of two groups (under or without anesthesia) using the system previously described.

The inclusion of the patient's procedure in the trial will be recorded by writing the name in the Clinical Judgment along with the group to which she belongs according to the randomization process. The patient will also be given the specific document of inclusion in the trial to sign after explaining what it consists of

and give him consent for the test. The documents will be sent for consultation according to the usual channels after filling in the surgical demand register appropriately as it is standardized in the unit.

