## **Summary of the Consent Delivery Procedure:**

- 1. Delivery and signature of the informed consent at the time of indication of the hysteroscopy.
- **2.** Explanation of the study and requirement of your signature for inclusion in the study, if the patient agrees to participate.
- **3.** Simple 1:1 randomization of patients using the random system proposed in the protocol. The patient's CH should be noted for the group to which she belongs.
- **4.** Explanation of the procedure again on the day of the intervention, ensuring that it is not mentioned if anesthesia will be used to avoid bias in the evaluation of pain.
- **5.** Collection of the signed consent in consultation, before the intervention, to confirm participation

This procedure ensures that all ethical and legal regulations are complied with, and that the study is conducted in a controlled manner, with minimal risk of bias, ensuring data integrity and the well-being of participating patients.

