#### **Content of informed consent:**

Informed consent should detail all relevant aspects of the study, including:

- The standard procedure for diagnostic hysteroscopy.
   Possible risks and benefits of the intervention.
- Description of the local anaesthesia to be administered in the relevant group, and the option of no anaesthesia in the control group and a placebo instead. It is important to mention this because the patient who does not receive anesthesia must wait for an intervention, otherwise, she could know that nothing is being administered.
- Confidentiality of the data and the conditions under which they will be used.
- Information about randomization in the study (whether or not anesthesia will be used), and that this decision will be made randomly.
- Delivery of the **STAI** (**State-Trait Anxiety Inventory**) **questionnaire**, which the patient must complete before the procedure.

As an important note: The professional in charge of delivering the information should try to influence the patient's expectations as little as possible, transmitting the information clearly, but avoiding both minimizing her possible fears and inducing them unnecessarily. That is, when explaining the procedure and the objective of the trial, it should be emphasized that there is no solid evidence that anesthesia is useful in this procedure and that, in fact, its use is not routinely standardized and that in many patients it is not administered. In addition, it will be emphasized that the objective is to demonstrate whether this practice, which can also be uncomfortable for the patient, could be avoided. They should be reassured, resolve their doubts and explain that most patients tolerate this procedure without anesthesia, however, they should not dwell too much on this aspect to minimize knowledge bias, since many patients forget irrelevant information when the day of the intervention arrives. In this way, the inherent fear that any patient has of a procedure that is painful before it is partially counteracted.

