## **Consent collection in hysteroscopy consultation:**

On the day of the intervention, the patient will deliver the signed informed consent, which was previously provided and explained.

The explanation of the procedure will be reiterated, including details about what will occur during the diagnostic hysteroscopy, but without mentioning whether or not anesthesia will be used. This is essential to avoid biases in the perception of pain, which could be influenced by prior knowledge of the intervention.

It will be ensured that the patient understands that consent has already been provided and that this is an additional step in the information process. The patient will be able to ask questions or express any concerns at this time.

If the patient asks if she will be given anesthesia, as it is a blinded trial, it is included in the document of the patient's participation in the trial, that the doctor may refrain from communicating to her which treatment group she is in, therefore, it is especially important that this group is hidden. However, again, an attempt will be made to reassure the patient, explaining that the procedure is usually well tolerated with and without anesthesia and that, in addition, routinely, the use of anesthesia may or may not be applied equally according to the criteria of the doctor performing the test, as there is no firm recommendation on its use. To further minimize bias, all patients will be fitted with the speculum to perform a correct vaginal and cervical examination and will be irrigated with saline solution in the control group as explained in the protocol.

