## **Patient Randomization**

## Randomization Method

For the assignment of the patient to the groups (with anesthesia or without anesthesia), a simple 1:1 randomization method will be used, which means that each patient has a 50% chance of being assigned to each group.

A completely random and reliable system will be used for patient allocation. https://www.random.org/, which allows you to generate assignments without bias.

A random number (between 1 and 100) will be assigned to each patient, and it will be established that the odd numbers correspond to the group with anesthesia (**Group A**) and the even numbers to the group without anesthesia (**Group B**). It will be noted in the Clinical Judgment.

Alternatively, a system of opaque bags with numbered papers can be used to perform randomization directly in the office, in case you prefer not to use software. (But preferably you should use the software if you can)

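### The draw is placed at the indication visit and the arm is noted in the record, so eligibility checks that can only be settled on the procedure day fall after randomisation

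*Protocol*

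**What the plan says.** **Timing.** The Randomization process section of the protocol states: "Randomization will be carried out at the time the patient presents for the intervention (in consultation, when the indication is made". The opening words could suggest the procedure day, but the parenthesis points to the indication visit. The Summary of the Consent Delivery Procedure agrees: the draw is step 3, and the procedure day first appears at step 4 ("Explanation of the procedure again on the day of the intervention").

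**Recording of the arm.** Step 3 adds: "The patient's CH should be noted for the group to which she belongs". Randomization Method says of the assignment: "It will be noted in the Clinical Judgment". Randomization process repeats the instruction and then forwards the paperwork through the unit's normal booking route.

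**Exclusions.** The list under Complex procedures, within the exclusion criteria, includes a wait of more than 60 minutes, analgesic intake before the test, and failure to supply consent or the anxiety scale. Content of informed consent hands out the STAI with the consent and describes it as a questionnaire "which the patient must complete before the procedure".

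**What happens to excluded patients.** Patients excluded from the study deletes the data of anyone rejected after inclusion but keeps the reason. Section 3.1, Analysis by Protocol, analyses completers only.

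**The concern.** When eligibility is closed before the arm is known, the arm cannot influence who is kept. Here the order is reversed for at least two criteria. Whoever applies them on the procedure day can look up the arm, and no section gives the decision to a masked person. The protocol itself names observer bias and selection bias as threats, and the outcome is self-reported pain.

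If the arm affected even a few of these decisions, the groups compared would no longer be the groups randomised. Because outcome data are deleted, the effect could not be corrected afterwards. The retained reasons would allow exclusions to be counted by arm and cause, but no more.

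The early chart note also adds some risk that the patient learns her arm. The consent collection section wants to avoid this and says "the doctor may refrain from communicating to her which treatment group she is in".

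**Working it through.** **1. Order of events**

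| Event | When | Where in the protocol |
|---|---|---|
| Consent signed | Indication visit | Consent summary, step 1; Randomization process |
| Draw, group noted in record | Indication visit | Consent summary, step 3; Randomization Method; Randomization process |
| Waiting time over 60 minutes | Procedure day | Complex procedures |
| Analgesic before the test | Procedure day | Complex procedures |
| STAI complete | Any time up to the procedure | Content of informed consent |
| Signed consent handed in | Procedure day | Consent summary, step 5; consent collection section |

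Two exclusions necessarily follow the draw, and a third does if the STAI is still incomplete. Consent itself should not be counted, because signature is already required before the draw.

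**2. Check of the method against the plan's own figure.** Inputs: difference 1.5, SD 2.0 (Clinically Relevant Difference), alpha 0.05, power 80%. With a two-sided t-test (the sidedness is not stated, but two-sided reproduces the result) and the noncentral t distribution, 28.9 patients per group are needed, so 29. Power at 29 per group is 80.1%. The plan's figure reproduces.

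**3. Size of a possible bias.** The protocol gives no exclusion rates, so the inputs here are assumptions: 1 or 2 of 35 patients in one arm are excluded selectively (35 is half of the upper recruitment figure of 70), and their pain lies d = 1 or 2 points from that of the patients retained.

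Shift in the arm mean = f × d, where f is the share excluded. Type I error is the two-sided rejection probability at alpha 0.05 with no true effect and SD 2.0.

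| f | d | Shift | Share of 1.5 | Type I error, 29 per group | Type I error, 35 vs 34 or 33 |
|---|---|---|---|---|---|
| 1/35 | 1 | 0.029 | 1.9% | 5.03% | 5.04% |
| 1/35 | 2 | 0.057 | 3.8% | 5.13% | 5.16% |
| 2/35 | 1 | 0.057 | 3.8% | 5.13% | 5.15% |
| 2/35 | 2 | 0.114 | 7.6% | 5.53% | 5.62% |

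For example, 2/35 × 2 = 0.114 points. At 35 versus 33 the standard error is 2.0 × √(1/35 + 1/33) = 0.485, so the noncentrality is 0.114/0.485 = 0.24, which barely moves the rejection rate.

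Over the protocol's SD range, the largest case gives 5.77% with SD 1.8 and 5.40% with SD 2.5. If exclusions are unrelated to arm, the shift is zero and only power is lost.

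**The case against.** The case for leaving this alone is strong on size. Waiting time is a clock reading, and prior analgesic intake is a fact about a patient who is meant not to know her arm. Both precede the procedure, so if they are checked then, nobody can select on pain not yet felt. Simple randomisation after consent remains unpredictable, and Possible limitations accepts that the operator knows the arm at treatment in any case. Much of the harm also comes from the rules that delete excluded patients; if those patients were kept and analysed, the timing of the draw would matter far less. All of this stands. It limits the priority of the point but does not remove it.

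Several stronger readings do not hold:

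- **Two rival timing rules.** A reader might infer this from the Randomization process sentence. The parenthesis and the consent summary agree on the indication visit; the sentence is loosely worded and needs an edit.
- **Consent obtained after the draw.** The step "Collection of the signed consent in consultation, before the intervention, to confirm participation" and the sentence "On the day of the intervention, the patient will deliver the signed informed consent" might suggest it. They describe handing in a form already signed.
- **A broken mask for the principal investigator.** Section 3.4 is undercut only if the principal investigator can read the record, and no section says so. Moving the draw would not cure it either, since the arm is recorded eventually.
- **A large false-positive rate.** Removing 20% of one arm selectively with a 2-point gap gives 0.20 × 2 = 0.4 points and 11.6% at 29 per group. Removing the highest-pain patients from one arm gives about 9%, 16% and 32% when 2, 4 and 7 of 35 are dropped. Nothing in the protocol suggests exclusion on that scale, and pre-procedure checks cannot pick out the highest-pain patients.

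**Conclusion.** The concern holds as a low-cost improvement. As written, two procedure-day exclusions, and a third if the STAI is outstanding, fall after randomisation with the arm readable by staff, and the affected patients leave the analysis. The protocol shows an open route to selection bias; it does not show that selection will occur.

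Under the assumed inputs the shift is 0.03–0.11 VAS points, or 2–8% of the 1.5-point target, with a type I error of 5.0–5.8%. This rests on few exclusions, a modest pain gap, and the checks being made before the procedure. The required 29 per group does not change.

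The point is secondary to the rules that remove excluded patients' data. Those rules also govern exclusions arising during the procedure (failed access, fluid balance above 1000 cc, major complications), which follow randomisation whenever the draw is made.

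**What to change.** - In the consent summary and Randomization process, state that the draw is made on the procedure day, after consent, STAI and the pre-procedure eligibility checks (waiting time, analgesic intake) are complete and recorded. This also removes the ambiguous timing phrase.
- In the consent summary, Randomization Method and Randomization process, delete the instructions to note the group before that point. Record only trial participation until the draw.
- Log each draw with date, time and patient ID. Either the existing software or the opaque-bag system already allowed will serve; a list prepared in advance is an option but not essential.

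**Cost.** Changed wording and a log. The booking paperwork changes, someone must make and log the draw in clinic, and the anaesthetic must be available for every participant because the arm is unknown until the day.

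**Limits.** This does not deal with exclusions during the procedure, which depend on changing the data-removal rules. Nor does it by itself secure the masking in section 3.4, which also requires that the principal investigator be kept from the recorded arm.

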## Complex procedures:

- Morcellator myomectomies: More complex surgical procedures, such as morcellator myomectomy, are excluded because of their level of invasion and difficulty, which could interfere with the isolated assessment of anesthesia-associated pain.
- Failure to access the uterine cavity: If adequate access to the uterine cavity is not achieved, the procedure is considered incomplete and the patient will be excluded from the study.
- Situations that prevent access to the cavity: Patients in whom hysteroscopy is failed, with cervical stenosis or other anatomical defects that completely prevent adequate access to the uterine cavity will be excluded.
- Long interventions with a large fluid passage or water balance above 1000 cc: In these cases the patient may experience additional pain due to other circumstances unrelated to the routine procedure.
- **Known uterine malformations**: Patients with uterine malformations (such as septate, unicornuate, or bicornuate uterus) will be excluded, as this could complicate access and interpretation of results, as well as affect pain tolerance during hysteroscopy.
- Waiting times longer than 60 minutes: It has been associated with an increase in pain according to the SEGO guideline for ambulatory hysteroscopy.
   Taking analgesic medication before the test: Taking medication before the test may alter the results.
- Major complication associated with the intervention: Uterine perforation, creation of false pathway or false endocervical pathway or intense bleeding (expressed as hemorrhage that requires additional maneuvers than usual for resolution).
- Failure to provide adequate informed consent in consultation or the anxiety assessment scale prior to the procedure.

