## Time of delivery:

The informed consent will be given to the patient at the time when the diagnostic hysteroscopy is indicated, that is, when it is decided that the patient will undergo this procedure in consultation.

The patient will receive written consent and will be given the necessary time to read it carefully, resolve any doubts with the medical staff and reflect on her participation in the study.

It will also be explained that the signing of consent is a prerequisite for the procedure and that participation in the study is voluntary, and can be withdrawn at any time without affecting your medical treatment.

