#### **Commitment to Ethics**

We assure you that this study will be carried out in accordance with the fundamental ethical principles of biomedical research, in particular the principles of respect for the autonomy of the patient, beneficence, non-maleficence, and justice. Informed consent will be obtained from all participants prior to their inclusion in the study, and they will be guaranteed the possibility of withdrawing at any time without this affecting their medical care.

be required and we thank you in advance for your time and consideration in reviewing this protocol.	We remain at the disposal of the Et	hics Committee to provide ar	ny additional information that may
	1	advance for your time and	d consideration in reviewing this

Sincerely,

Date: 02/19/2025

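### Consent is meant to precede randomisation, but the protocol does not make a signed trial document held by the site a condition of the draw

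*Protocol*

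**What the plan says.** Four places in the protocol put the signature first.

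- Summary of the Consent Delivery Procedure starts at step 1 with "Delivery and signature of the informed consent at the time of indication of the hysteroscopy", requires a signature for inclusion at step 2, and reaches "Simple 1:1 randomization of patients using the random system proposed in the protocol" at step 3.
- The first sentence of Randomization process places the draw after the patient has read and signed.
- The annex section Informed Consent requires a signature before inclusion.
- Commitment to Ethics states: "Informed consent will be obtained from all participants prior to their inclusion in the study".

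Other places are looser.

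- Time of delivery hands over the form at the indication visit and lets the patient take time over it. It sets no limit relative to the draw.
- Step 5 of the same summary, two steps after randomisation, is "Collection of the signed consent in consultation, before the intervention, to confirm participation".
- Consent collection in hysteroscopy consultation says "On the day of the intervention, the patient will deliver the signed informed consent, which was previously provided and explained".
- The exclusion list under Complex procedures includes "Failure to provide adequate informed consent in consultation or the anxiety assessment scale prior to the procedure".
- Randomization process names both arrival for the intervention and the indication visit as the moment of the draw. It then describes entering the group in the Clinical Judgment, and next says "The patient will also be given the specific document of inclusion in the trial to sign after explaining what it consists of".

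On voluntariness, Time of delivery says that "the signing of consent is a prerequisite for the procedure" and, in the same sentence, that taking part is voluntary. Content of informed consent lists the two arms and the randomisation among the contents of that consent.

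Patients excluded from the study removes all data of anyone rejected after inclusion, keeping only the reason. Analysis by Protocol analyses completers only.

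**The concern.** Randomisation protects the comparison only if entry to the trial is settled before the arm is known. Here the draw is made in clinic, the group is written in the record, the treating doctor knows the arm, and the endpoint is a self-reported pain score. If a signature is still outstanding when the group is on record, what staff say about the trial, or how firmly they pursue the missing form, can depend on the arm. A patient who then does not sign becomes a post-randomisation loss. Widening the analysis set would not repair this, because a patient who has not consented has no data that the trial may use.

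The prerequisite wording raises a second issue. A patient could reasonably conclude that her hysteroscopy depends on joining the trial.

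**Working it through.** This is mainly a question of sequence, so the passages are set against each other first. The arithmetic follows, for scale only.

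**1. Which document must be signed before the draw?** Randomization process uses two terms: an informed consent, signed before the draw, and a trial-specific inclusion document, mentioned after the draw and the group entry. It also refers to consent for the test itself. It does not say whether the consent required before the draw is the hysteroscopy consent, the trial document or both. If it is the hysteroscopy consent, this section gives the trial document no fixed place before allocation.

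**2. When is the draw?** The same sentence names two visits. If the draw is at the indication visit, as steps 1 to 3 of the summary imply, then collection at step 5 and delivery on the procedure day both come after it.

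**3. Must the site hold the signed form at the draw?** No passage says so. Time to reflect is given, the form comes back on the procedure day, and nothing makes the draw wait for it.

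**4. When does the consent exclusion act?** It is judged in consultation. Step 5 and the consent-collection section use that term for the procedure day, while Randomization process uses it for the indication visit. On the first reading the exclusion falls after an indication-visit draw.

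**5. What happens to a patient lost this way?** Her data are removed and she is outside the completers analysis.

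**6. Sample size reproduced.** Inputs are a difference of 1.5 and SD of 2.0 (Clinically Relevant Difference), alpha 0.05, taken as two-sided because the protocol does not say, and power 0.80. The effect size is d = 1.5 / 2.0 = 0.75. The noncentral t calculation gives 28.9, so 29 per group and 58 in total, with power 0.801. This matches Final Estimate. The 64 to 70 range is 58 × 1.10 = 63.8 and 58 × 1.20 = 69.6.

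**7. Non-return alone.** The protocol gives no rate, so 5 to 10% is an assumption.

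| Randomised | Non-return | Remaining | Power |
|---|---|---|---|
| 64 | 5% | 64 × 0.95 = 60.8 | 0.820 |
| 64 | 10% | 64 × 0.90 = 57.6 | 0.799 |
| 70 | 5% | 70 × 0.95 = 66.5 | 0.854 |
| 70 | 10% | 70 × 0.90 = 63.0 | 0.834 |

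Keeping 58 evaluable patients tolerates a total loss of 1 − 58/64 = 9.4% from 64, or 1 − 58/70 = 17.1% from 70. On these assumptions the planned power is essentially kept.

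**8. Bias, by formula only.** If a fraction p of one arm is removed and would have scored δ points differently from those who stay, that arm's mean shifts by p × δ. With δ = 2, p = 5% gives 0.1 and p = 10% gives 0.2, against a target difference of 1.5. Both inputs are assumed, and equal selection in both arms would cancel. This shows the mechanism and is not an estimate.

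**The case against.** The strongest reply is that no passage puts the draw before the signature. The summary and Randomization process both state the correct order outright. The paragraph with the inclusion document can be read as a list of paperwork: its link word is additive, and its only statement of order ties signing to the explanation, not to the draw. The procedure-day section speaks of a form already signed, and adds that consent has by then been given. The word prerequisite may refer to the ordinary hysteroscopy consent. The patient consent form was not available for this review, so its own wording cannot be judged.

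All of this stands, and it rules out three stronger readings.

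- A reader might infer that staff are instructed to randomise first, or that whoever explains the trial document already knows the arm. Both rest on the order of sentences, not on a stated rule.
- A reader might infer that delivery on the procedure day proves late signing. It does not.
- A reader might add 5 to 10% non-return to the 10 to 20% loss allowance and report 46 to 60 patients and 70 to 81% power. The rate is assumed. The pain score is taken on the procedure day, so the allowance plausibly already covers losses between draw and procedure. The low end also pairs 64 patients, which is the 10% inflation, with a 20% loss.

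The reply does not supply a rule that the site must hold the signed trial document before allocating. Nor does it resolve the two moments for the draw or the two documents.

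**Conclusion.** The point holds as a defect of sequence and wording. The intended order is clear, but the operating steps leave open a path in which a patient is allocated, with her group recorded, before the site holds her signed trial document. Non-signers would then disappear from the trial, possibly at different rates by arm. The main risk is selection bias. Its size cannot be derived from the protocol, and no loss of power should be claimed. The conclusion assumes that some patients use the time to reflect and return the form after an indication-visit draw, which the text permits but does not require.

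The conflict over voluntariness does not depend on how Randomization process is read. The prerequisite wording and the list of consent contents cannot both stand beside voluntary participation without saying which consent is meant. The removal of data and the completers-only analysis are separate matters that re-ordering the consent steps would not settle.

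**What to change.** - In Summary of the Consent Delivery Procedure, Consent collection in hysteroscopy consultation and Randomization process, state one order and one time for the draw: explain the trial, sign the trial-specific document, site holds the signed document, then generate the allocation. A patient who wants time to reflect is drawn only once the signed document is back.
- Name the two documents consistently and say that the trial-specific one is the condition of the draw.
- Keep the procedure-day step only as confirmation that consent still stands.
- Apply the consent item of the exclusion list before the draw.
- In Time of delivery, say that only the hysteroscopy consent is needed for the procedure and that declining the trial does not affect care.

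The cost is re-ordering existing steps and a few sentences of wording. Some draws will happen slightly later. No extra patients or procedures are needed.
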